Attachment 8:	Details for Pharmacokinetic Sampling and Collection of Food Intake Information	129

LIST OF IN-TEXT TABLES AND FIGURES**TABLES**

Table 1:	Summary of Efficacy Evaluations	21
Table 2:	Investigational Product and its Metabolites	33
Table 3:	NOAEL Doses of ALS-008176 and Exposure of ALS-008112 in Adult and Juvenile Rats and Dogs After Repeated Dosing of ALS-008176	35
Table 4:	Pharmacokinetic Parameters of ALS-008112 Following a Single Oral Dose of 1,000 mg ALS-008176 in Subjects With Different Degrees of Renal Function	38
Table 5:	Projected Plasma Exposures of ALS-008112 at the Proposed Dose Regimens	52
Table 6:	Ordinal Scale on Day 5/6 (Depending on the Timing of the LD Administration)	83

FIGURES

Figure 1:	Schematic Overview of Part 1 of the Study	50
Figure 2:	Schematic Overview of Part 2 of the Study	50
Figure 3:	Two Scenarios for the Timing of Collection of Nasal Swabs and Endotracheal Samples (if Intubated).....	66

PROTOCOL AMENDMENTS

Amendments below are listed beginning with the most recent amendment.

Amendment 4 (This document)

This amendment is considered to be substantial based on the criteria set forth in Article 10(a) of Directive 2001/20/EC of the European Parliament and the Council of the European Union.

The overall reason for the amendment: The overall reason for the amendment is for Part 2 of the study (1) to include additional safety samples for biochemistry, (2) to lift the requirement for triplicate electrocardiograms (ECGs) and reduce the ECG timepoints, (3) to prohibit the use of P-glycoprotein (P-gp) inhibitors and inducers, and (4) to optimize the pharmacokinetic (PK) sampling scheme.

The table below gives an overview of the rationale for each change and all applicable sections.

Rationale: Based on the observed exposure levels and safety/tolerability data generated in Part 1 of the study, the dose regimen for Part 2 of the study will remain unchanged.

SYNOPSIS

[3.1 Overview of Study Design](#)

[3.2 Study Design Rationale](#)

Rationale: In Part 2 of the study, additional safety samples for biochemistry will be collected on Day 2, Days 3-6, and Day 10, to better characterize the clinical observations of isolated, asymptomatic elevations of aspartate aminotransferase (AST)/alanine aminotransferase (ALT) (without concomitant elevations of the bilirubin levels) observed in Part 1 of the study.

[Time and Events Schedule](#)

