-chloride	-total (direct and indirect) bilirubin

Urinalysis

Dipstick	Sediment (if dipstick result is abnormal)
-specific gravity	-RBCs
-pH	-WBCs
-glucose	-epithelial cells
-protein	-crystals
-blood	-casts
-ketones	-bacteria
-bilirubin	
-urobilinogen	
-nitrite	
-leukocyte esterase	

Dipstick will be performed as per the [Time and Events Schedule](#). If dipstick is abnormal, microscopic evaluation should be performed, with evaluation of sediment as listed above.

In the microscopic examination, observations other than the presence of WBCs, RBCs, and casts may also be reported by the laboratory and need to be captured in the eCRF.

Other:

- Calculation of estimated GFR (CKD-EPI equation).
- Urine pregnancy testing for all female subjects.

Sites should attempt to collect all safety labs as defined in this protocol. In some instances, individual laboratory assessments are not routinely run at a local site. If it is not practical to obtain the results for a particular assessment due to local considerations, the sponsor study responsible physician or delegate may on a case by case basis permit individual sites to not collect that assessment.

Electrocardiogram

In Part 1 of the study, triplicate 12-lead ECGs (three 10-s recordings at approximately 60-s intervals) will be collected and analyzed by a central laboratory at screening, on Day 1, on Day 7, on Day 28, and when clinically indicated. On Day 1, triplicate ECGs will be collected at 2 time points: approximately 30 to 60 minutes and 3 to 6 hours after the LD. If an ECG is abnormal at Day 7, an additional ECG should be performed at Day 14.

In Part 2 of the study, a single 12-lead ECG will be collected and analyzed by a central laboratory at screening, on Day 4 (for subjects who remain hospitalized at this time), on Day 28, and when clinically indicated. If discharged earlier than Day 4, the subject needs to have an ECG recorded on the day of discharge. The ECG will be performed 30 minutes to 3 hours after the first dose of study drug of that day.

During the collection of ECGs, subjects should be in a quiet setting without distractions (eg, television, cell phones). Subjects should rest in a supine position for at least 5 minutes before ECG collection and should refrain from talking or moving arms or legs. If blood sampling

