11.10. Safety Analyses

Safety data will be presented descriptively. No statistical testing of safety data is planned. For safety, baseline is defined as the last assessment prior to the first intake of study drug.

Adverse Events

The verbatim terms used in the eCRF by investigators to identify AEs will be coded using the Medical Dictionary for Regulatory Activities. Treatment-emergent AEs are AEs with onset during the treatment phase or that are a consequence of a preexisting condition that has worsened since baseline. All reported AEs will be included in the analysis. For each AE, the percentage of subjects who experience at least 1 occurrence of the given event will be summarized by treatment group. In addition, comparisons between treatment groups will be provided if appropriate.

Summaries, listings, datasets, or subject narratives may be provided, as appropriate, for those subjects who die, who discontinue treatment due to an AE, or who experience a severe AE or an SAE.

Clinical Laboratory Tests

Laboratory data will be summarized by type of laboratory test. Reference ranges and markedly abnormal results (specified in the SAP) will be used in the summary of laboratory data. Descriptive statistics will be calculated for each laboratory analyte at baseline and for observed values and changes from baseline at each scheduled time point. Changes from baseline results will be presented in pre- versus posttreatment cross-tabulations (with classes for below, within, and above normal ranges). Frequency tabulations of the abnormalities will be made. A listing of subjects with any laboratory results outside the reference ranges will be provided. A listing of subjects with any markedly abnormal laboratory results will also be provided.

The laboratory abnormalities will be determined according to the criteria specified in the draft Division of Microbiology and Infectious Diseases Adult Toxicity Table (see [Attachment 1](#)) and in accordance with the normal ranges of the clinical laboratory if no gradings are available.

Electrocardiogram

The effects on cardiovascular variables will be evaluated by means of descriptive statistics and frequency tabulations. These tables will include observed values and changes from baseline values at each scheduled time point (the predose ECG will be used as baseline). Frequency tabulations of the abnormalities will be made.

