Hyperbilirubinemia (when accompanied by any increase in other liver function test)	1.1 - <1.25 x ULN	1.25 - <1.5 x ULN	1.5 – 1.75 x ULN	> 1.75 x ULN
Hyperbilirubinemia (when other liver function are in the normal range)	1.1 - <1.5 x ULN	1.5 - <2.0 x ULN	2.0 – 3.0 x ULN	> 3.0 x ULN
BUN	1.25 - 2.5 x ULN	2.6 - 5 x ULN	5.1 - 10 x ULN	> 10 x ULN
Hyperuricemia (uric acid)	7.5 – 10.0 mg/dL	10.1 – 12.0 mg/d L	12.1 – 15.0 mg/d L	>15.0 mg/d L
Creatinine	1.1 - 1.5 x ULN	1.6 - 3.0 x ULN	3.1 - 6 x ULN	> 6 x ULN or dialysis required

ENZYMES				
	Grade 1	Grade 2	Grade 3	Grade 4
AST (SGOT)	1.1 - <2.0 x ULN	2.0 – <3.0 x ULN	3.0 – 8.0 x ULN	> 8 x ULN
ALT (SGPT)	1.1 - <2.0 x ULN	2.0 – <3.0 x ULN	3.0 – 8.0 x ULN	> 8 x ULN
GGT	1.1 - <2.0 x ULN	2.0 – <3.0 x ULN	3.0 – 8.0 x ULN	> 8 x ULN
Alkaline Phosphatase	1.1 - <2.0 x ULN	2.0 – <3.0 x ULN	3.0 – 8.0 x ULN	> 8 x ULN
Amylase	1.1 - 1.5 x ULN	1.6 - 2.0 x ULN	2.1 - 5.0 x ULN	> 5.1 x ULN
Lipase	1.1 - 1.5 x ULN	1.6 - 2.0 x ULN	2.1 - 5.0 x ULN	> 5.1 x ULN

URINALYSIS				
	Grade 1	Grade 2	Grade 3	Grade 4
Proteinuria	1+ or 200 mg - 1 gm loss/day	2-3+ or 1- 2 gm loss/day	4+ or 2-3.5 gm loss/day	nephrotic syndrome or > 3.5 gm loss/day
Hematuria	microscopic only <10 rbc/hpf	gross, no clots >10 rbc/hpf	gross, with or without clots, OR red blood cell casts	obstructive or required transfusion

CARDIOVASCULAR				
	Grade 1	Grade 2	Grade 3	Grade 4
Cardiac Rhythm		asymptomatic, transient signs, no Rx required	recurrent/persistent; symptomatic Rx required	unstable dysrhythmia; hospitalization and treatment required
Hypertension	transient increase > 20 mm/ Hg; no treatment	recurrent, chronic increase > 20mm/ Hg. /treatment required	acute treatment required; outpatient treatment or hospitalization possible	end organ damage or hospitalization required
Hypotension	transient orthostatic hypotension with heart rate increased by <20 beat/min or decreased by <10 mm Hg systolic BP, No treatment required	symptoms due to orthostatic hypotension or BP decreased by <20 mm Hg systolic; correctable with oral fluid treatment	requires IV fluids; no hospitalization required	mean arterial pressure <60mm/ Hg or end organ damage or shock; requires hospitalization and vasopressor treatment
Pericarditis	minimal effusion	mild/ moderate asymptomatic effusion, no treatment	symptomatic effusion; pain; EKG changes	tamponade; pericardiocentesis or surgery required

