4.3.2. Clinical Laboratory Tests

Laboratory parameters of hematology, serum chemistry and urinalysis will be investigated: All analyses will be done on SI-converted values as available in the database.

Unifying multiple laboratory values by standardization:

Since local labs are used, the SI-converted values will be standardized using the following formula and using the phantom laboratory generalized lab norms (GLN) as proposed by Francis Ruvuna, David Flores et al.^[13]

$$y = (x - Li) * \frac{Ucs - Lcs}{Ui - Li} + Lcs$$

Where

y = the transformed individual analyte value to a common standard laboratory reference range;

x = the original value;

L_i and U_i = lower and upper limits of normal for individual laboratory analyte;

L_{cs} and U_{cs} =lower and upper limit for the selected common standard laboratory or phantom laboratory GLN proposed by Francis Ruvana et all. [13]

The standardized values, with the phantom laboratory GLN will be used during the analysis.

Toxicity grades and abnormalities for laboratory parameters:

Toxicity grades will be computed according to the DMID adult toxicity grading list (see attachment at the end of this document). In case different grades are available for fasted/non fasted results, the results are assumed to be taken in the condition as specified in the protocol (i.e. not necessarily according to possible remarks indicating a deviation to this). If no condition is specified in the protocol, the non-fasting gradings should be used.

In case no toxicity grades are defined for any laboratory test, then non-graded abnormalities (high/low vs. normal range) will be used instead.

The worst grade over the whole observational period (treatment) will be determined.

Treatment-emergent definition for toxicity grades and abnormalities

An abnormality (toxicity grade or abnormality based on normal ranges) will be considered treatment-emergent in a particular phase if it is worse than the baseline value. If the baseline is missing, the abnormality is always considered as treatment-emergent. A shift from “abnormally low” at reference to “abnormally high” post reference (or vice versa) is also treatment-emergent. The treatment emergent definition is applicable in both, the treatment and follow-up phase.

Special assessments:

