$$\text{GFR}(\text{mL}/\text{min}/1.73 \text{ m}^2) = 141 \times \text{minimum}(\text{CREAT} / \text{K} ; 1)^\alpha \times \text{maximum}(\text{CREAT} / \text{K} ; 1) \cdot 1.209 \times 0.993^{\text{Age}} \times (1.018 \text{ IF SEX} = \text{'F'}) \times (1.159 \text{ IF RACEGR1} = \text{'BLACK'})$$

Where:

CREAT= Serum Creatinine

Unit CREAT = mg/dL.

Conversion CREAT: mg/dL = $\mu\text{mol}/\text{L} / 88.4$

Unit WEIGHT = kg, unit HEIGHT = cm

Use last measurement before intake for weight and height (baseline).

Use age at screening.

$K = 0.7 \text{ IF SEX} = \text{'F'}$ or $0.9 \text{ IF SEX} = \text{'M'}$

$\alpha = -0.329 \text{ IF SEX} = \text{'F'}$ or $-0.411 \text{ IF SEX} = \text{'M'}$

With the following scores:

Grade 0: $\text{GFR} > 60 \text{ mL}/\text{min}/1.73\text{m}^2$ (grade 0);

Grade 1: $30 \text{ mL}/\text{min}/1.73\text{m}^2 < \text{GFR} \leq 60 \text{ mL}/\text{min}/1.73\text{m}^2$

Grade 2: $15 \text{ mL}/\text{min}/1.73\text{m}^2 < \text{GFR} \leq 30 \text{ mL}/\text{min}/1.73\text{m}^2$

Grade 3: $\text{GFR} \leq 15 \text{ mL}/\text{min}/1.73\text{m}^2$

Analysis Methods

Actual values and change from baseline will be summarized by treatment group at each scheduled time point.

The number and percentage of subjects will be shown in a cross-tabulation of the toxicity/abnormality post-baseline versus baseline at each scheduled time point.

Additionally, a cross-tabulation of the worst toxicity/abnormality versus baseline will be presented per phase (Treatment phase, Follow-up phase) and for the combination of Treatment and Follow-up phase. This table will also show the number and percentage of subjects per worst toxicity/abnormality, the number and percentage of subjects per treatment-emergent worst toxicity/abnormality and the cumulative number of subjects per treatment-emergent toxicity/abnormality or worse.

Mean \pm SE graphs over time for the actual values and changes from reference will be generated for all tests performed.

A listing of abnormal individual subject hematology and clinical chemistry values from scheduled and unscheduled time points will be provided. This listing will include all other time points for the corresponding subject/parameter.

Grade 2 or higher toxicity laboratory values will be listed separately.

Urinalysis results will be listed. Proteinuria and urine WBCs will be summarized.

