ATTACHMENT

DMID ADULT TOXICITY GRADES FOR LABORATORY PARAMETERS

PARAMETER	Unit	GRADE 1	GRADE 2	GRADE 3	GRADE 4
Hemoglobin	g/dL	10.5 – 9.5	<9.5 – 8.0	<8.0 – 6.5	<6.5
Absolute Neutrophil Count	GIGA/L	1.50 – 1.00	<1.00 – 0.75	<0.75 – 0.50	<0.50
Platelets	GIGA/L	<100 – 75	<75 – 50	<50 – 20	<20
WBC, high	GIGA/L	11 – <13	13 – <15	15 – 30	>30
WBC, low	GIGA/L	1 – <4			<1
Fibrinogen, high	mg/dL	400 – 600	>600		
	µmol/L	11.76 – 17.65	>17.65		
Fibrinogen, low	mg/dL	200 – 100	<100 – 50	<50	
	µmol/L	5.88 – 2.94	<2.94 – 1.47	<1.47	
Prothrombin Time		>1.00 x ULN – 1.25 x ULN	>1.25 x ULN – 1.50 x ULN	>1.50 x ULN – 3.00 x ULN	>3.00 x ULN
Activated Partial Thromboplastin Time		>1.00 x ULN – 1.66 x ULN	>1.66 x ULN – 2.33 x ULN	>2.33 x ULN – 3.00 x ULN	>3.00 x ULN
AST		>1.0 x ULN – <2.0 x ULN	2.0 x ULN – <3.0 x ULN	3.0 x ULN – 8.0 x ULN	>8.0 x ULN
ALT		>1.0 x ULN – <2.0 x ULN	2.0 x ULN – <3.0 x ULN	3.0 x ULN – 8.0 x ULN	>8.0 x ULN
GGT		>1.0 x ULN – <2.0 x ULN	2.0 x ULN – <3.0 x ULN	3.0 x ULN – 8.0 x ULN	>8.0 x ULN
Alkaline Phosphatase		>1.0 x ULN – <2.0 x ULN	2.0 x ULN – <3.0 x ULN	3.0 x ULN – 8.0 x ULN	>8.0 x ULN
Amylase		>1.0 x ULN – 1.5 x ULN	>1.5 x ULN – 2.0 x ULN	>2.0 x ULN – 5.0 x ULN	>5.0 x ULN
Lipase		>1.0 x ULN – 1.5 x ULN	>1.5 x ULN – 2.0 x ULN	>2.0 x ULN – 5.0 x ULN	>5.0 x ULN
Hyponatremia	mEq/L mmol/L	135 – 130	<130 – 123	<123 – 116	<116
Hypernatremia	mEq/L mmol/L	146 – 150	>150 – 157	>157 – 165	>165
Hypokalemia	mEq/L mmol/L	3.4 – 3.0	<3.0 – 2.5	<2.5 – 2.0	<2.0
Hyperkalemia	mEq/L mmol/L	5.6 – 6.0	>6.0 – 6.5	>6.5 – 7.0	>7.0
Hypoalbuminemia	g/dL	<LLN – 3	<3 – 2	<2	
Hypoglycemia	mg/dL	64 – 55	<55 – 40	<40 – 30	<30
	mmol/L	3.55 – 3.05	<3.05 – 2.22	<2.22 – 1.67	<1.67
Hyperglycemia	mg/dL	116 – 160	>160 – 250	>250 – 500	>500
	mmol/L	6.44 – 8.88	>8.88 – 13.88	>13.88 – 27.75	>27.75
Hypocalcemia (corr. for albumin)	mg/dL	8.4 – 7.8	<7.8 – 7.0	<7.0 – 6.1	<6.1
	mmol/L	2.10 – 1.95	<1.95 – 1.75	<1.75 – 1.52	<1.52
Hypercalcemia (corr. for albumin)	mg/dL	10.6 – 11.5	>11.5 – 12.5	>12.5 – 13.5	>13.5
	mmol/L	2.64 – 2.87	>2.87 – 3.12	>3.12 – 3.37	>3.37
Hypomagnesemia	mEq/L	1.4 – 1.2	<1.2 – 0.9	<0.9 – 0.6	<0.6
	mmol/L	0.70 – 0.60	<0.60 – 0.45	<0.45 – 0.30	<0.30
Hypophosphatemia	mg/dL	2.4 – 2.0	<2.0 – 1.5	<1.5 – 1.0	<1.0
	mmol/L	0.77 – 0.65	<0.65 – 0.48	<0.48 – 0.32	<0.32
Hyperbilirubinemia (TB)		>1.0 x ULN – <1.5 x ULN	1.5 x ULN – <2.0 x ULN	2.0 x ULN – 3.0 x ULN	>3.0 x ULN

PARAMETER	Unit	GRADE 1	GRADE 2	GRADE 3	GRADE 4

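### The SAP omits the protocol's stricter bilirubin grades for patients with another raised liver test, so values of 1.25 to 3.0 x ULN are graded one or two grades too low

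*SAP*

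**What the plan says.** **Protocol.** Section 11.10 (Safety Analyses, Clinical Laboratory Tests) names the governing table: "The laboratory abnormalities will be determined according to the criteria specified in the draft" DMID adult table, reproduced in Attachment 1. The chemistry part of that table grades bilirubin in two rows. One is headed "Hyperbilirubinemia (when accompanied by any increase in other liver function test"; the other is for bilirubin raised while the other liver tests are normal. The first has the lower cut-offs.

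**SAP.** Section 4.3.2 points to a different copy: "Toxicity grades will be computed according to the DMID adult toxicity grading list (see attachment at the end of this document". That attachment is titled as DMID adult grades, but it has only one bilirubin row, "Hyperbilirubinemia (TB", with no condition on any other test.

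The grades feed several outputs in Section 4.3.2. These are the baseline-to-visit cross-tabulations, the worst-grade tables by phase, and the treatment-emergent counts, where an abnormality "will be considered treatment-emergent in a particular phase if it is worse than the baseline value". There is also a separate listing: "Grade 2 or higher toxicity laboratory values will be listed separately".

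**The concern.** Both documents claim the same grading system, but they give different grades for the same bilirubin value when another liver test is raised. The SAP does not say that the stricter row was removed, so a reader of a table labelled DMID would not know.

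What is at stake is how combined liver abnormalities are described. Amendment 4 added Part 2 biochemistry samples to characterise AST/ALT elevations that were "without concomitant elevations of the bilirubin levels) observed in Part 1 of the study". The omission therefore does not touch the Part 1 signal. An accompanied bilirubin rise in Part 2 would be new information, and the SAP's tables would show it at a lower grade than the protocol's.

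**Working it through.** There is no sample-size or error-rate figure to reproduce. The check applies the three sets of limits to the same bilirubin values.

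**Inputs** (multiples of ULN)

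| Row | Grade 1 | Grade 2 | Grade 3 | Grade 4 |
|---|---|---|---|---|
| Protocol Attachment 1, another liver test raised | 1.1 to <1.25 | 1.25 to <1.5 | 1.5 to 1.75 | >1.75 |
| Protocol Attachment 1, other liver tests normal | 1.1 to <1.5 | 1.5 to <2.0 | 2.0 to 3.0 | >3.0 |
| SAP Attachment, single row | >1.0 to <1.5 | 1.5 to <2.0 | 2.0 to 3.0 | >3.0 |

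**Method.** Each row was treated as a step function and evaluated on a fine grid from ULN to above 3.0 x ULN. The difference is the SAP grade minus the protocol grade.

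**Another liver test raised**

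| Bilirubin (x ULN) | Protocol | SAP | Difference |
|---|---|---|---|
| >1.0 to <1.1 | none | 1 | +1 |
| 1.1 to <1.25 | 1 | 1 | 0 |
| 1.25 to <1.5 | 2 | 1 | -1 |
| 1.5 to 1.75 | 3 | 2 | -1 |
| >1.75 to <2.0 | 4 | 2 | -2 |
| 2.0 to 3.0 | 4 | 3 | -1 |
| >3.0 | 4 | 4 | 0 |

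**Other liver tests normal.** The SAP is one grade higher at >1.0 to <1.1 and identical from 1.1 upward.

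**Effect on the outputs**

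- *Grade 2+ listing.* Only accompanied values of 1.25 to <1.5 drop out, since they are grade 2 by the protocol and grade 1 by the SAP. Accompanied values from 1.5 upward stay in, those up to 3.0 at a lower grade.
- *Grade 4 counts.* Accompanied values above 1.75 and up to 3.0 are grade 4 by the protocol but grade 2 or 3 by the SAP.
- *Treatment-emergent status.* Take a baseline of 1.2 x ULN with normal ALT, followed by 1.4 x ULN with raised ALT. The protocol table gives grade 1 then grade 2, which is treatment-emergent. The SAP gives grade 1 both times, which is not.

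**Can the condition be evaluated?** Yes. The serum chemistry panel in protocol Section 9.7 lists ALT, AST and alkaline phosphatase together with "total (direct and indirect) bilirubin".

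**The case against.** The case for treating this as a minor documentation point has several parts.

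- *Reach.* No statistical testing of safety data is planned. Eligibility (Section 4.2) and discontinuation (Section 9.7.1) use ULN multiples directly and do not depend on the grade. This stands, and it limits the concern to descriptive reporting.
- *Visibility.* Actual values, changes from baseline and a listing of abnormal values are all planned, and ALT, AST and alkaline phosphatase have their own grades. So a combined pattern can be found by a reader who looks for it. This also stands, but the summary tables and counts rest on grades, and those would be lower.
- *Standardization.* SAP Section 4.3.2 maps local values linearly onto a common reference range, which preserves multiples of ULN only if the ratio of lower to upper limit is the same in both ranges. As an assumed illustration, take 1.7 x ULN locally. If that ratio is 0.15 locally and 0 in the common range, it becomes (1.7 - 0.15)/(1 - 0.15) = 1.82. In the reverse case it becomes 1.7 x 0.85 + 0.15 = 1.60 after rounding. The bands above therefore compare the tables and do not predict individual patients' grades. The two tables still conflict on whichever scale is graded.
- *General simplification.* The SAP attachment adapts DMID elsewhere. Grade 1 starts at >1.0 instead of 1.1 x ULN for the liver enzymes, for example, and the clinical qualifiers in the sodium rows are dropped. The single bilirubin row may belong to the same effort. Dropping a clinical qualifier is understandable where laboratory data cannot supply it. Here the condition is a laboratory result from the same panel.
- *Side effect of two rows.* Bilirubin falling from 1.7 x ULN alone (grade 2) to 1.6 with ALT just above ULN (grade 3) would count as worsening although bilirubin fell. This is a real drawback of the protocol's scheme and a possible reason for a single row. The SAP does not give it.

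**Conclusion.** The concern holds. The SAP's grading rule contradicts protocol Section 11.10 for bilirubin accompanied by another raised liver test. It under-grades by one grade from 1.25 to 1.75 and from 2.0 to 3.0 x ULN, and by two grades between 1.75 and 2.0. It over-grades by one at >1.0 to <1.1, whatever the other liver tests show.

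These sizes follow from the two tables alone and assume the same multiple of ULN is graded under each. The number of patients affected is unknown. It depends on how often bilirubin rises with another liver test in Part 2 and on how that trigger is defined.

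The SAP should be corrected before database lock. The consequence is confined to descriptive safety tables, and no efficacy conclusion or patient-level rule changes.

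**What to change.** Add the protocol's accompanied-bilirubin row to the SAP attachment (grade 2 at 1.25 to <1.5, grade 3 at 1.5 to 1.75, grade 4 at >1.75 x ULN), and apply the present row only when the other liver tests are normal. Three details need writing down:

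1. **Trigger.** Attachment 1 does not define which tests count or how large an increase is needed. One workable definition is ALT, AST or alkaline phosphatase above ULN at the same time point.
2. **Missing tests.** State which row applies when those results are absent. Section 9.7 lets the sponsor excuse individual sites from particular assessments, so this can happen.
3. **Grade 1 lower limit.** Use one limit in both rows, either >1.0 or 1.1 x ULN. The former matches the SAP's liver-enzyme rows; the latter matches Attachment 1.

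A table footnote should say that a bilirubin grade can change because another liver test has changed.

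If the single row is intended, the alternative is to say so in the SAP and justify it as a departure from protocol Section 11.10.

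The cost is one table row, a short definition and a conditional derivation in the programming. The tests are already in the scheduled chemistry panel.
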